## 9. DATA ANALYSIS/METHODS

**Analytic Plan.** We will use Mplus (Version 7.20) to conduct our analyses. Descriptive statistics (e.g. proportions for dichotomous variables, means, and standard deviations) will be calculated for all measures of interest. Outliers will be examined and kept in final analyses, unless substantial evidence is available for their deletion (e.g., data errors). When testing statistical hypotheses, statistical model assumptions will be examined.

**Aim 1: Determine the feasibility and acceptability of the SCThrive intervention for adolescents and young adults with SCD.** **Feasibility** of SCThrive will be assessed by the proportion of eligible patients approached for the study who consent to participate and attend at least 4/6 sessions. **Acceptability** will be assessed by qualitative analysis of focus groups at the end of treatment. The focus groups will elicit the AYAs overall impression of the program, the mixed format, how well they perform skills, and the progression of activities, as well as content- and format-specific feedback on the integration of iManage and SCD content, interest level, and length of sessions.

**Aim 2: Conduct a pilot randomized trial (final N=54 assuming 15% attrition) to determine whether the refined SCThrive intervention is superior to attention control in improving BA in AYAs with SCD ages 13-21.** A 2 (group; treatment vs. control) by 2 (time; Pre-/Post-test) mixed ANCOVA analysis will be used, with BA (PAM-13) as our primary outcome, time and group as main effects, and a time\*group interaction effect, to determine the needed effect size estimates. The statistical test of the interaction will be the primary tests of the efficacy of the SCThrive intervention. If statistically significant, the group\*time interaction would indicate BA changed differently across time between the two groups and effect sizes (d) will be calculated

for all significant simple main effects and simple comparison effect size calculations described above.

**Exploratory Aim:** A MANOVA will be used to test for significant group (*SCThrive* vs. attention control) differences on improvements in self-management behaviors and quality of life scores at three months. A significant omnibus test will be followed with simple comparisons and computation of effect size estimates (d).

**Power Analysis:** We chose the PAM-13 (BA) as our primary outcome for power estimates because the General Linear Modeling analyses found a significant improvement in PAM-13 means from pre-test to post-test for the in-person self-management versus the self-management online portal groups, whereas the responsiveness of the other measures (e.g. SCD quality of life) may require a longer time-frame. The average effect size (eta-squared) for the change in BA was  $\eta^2 = 0.14$ , which is a large effect. A 2 (treatment vs. control) by 2 (pre-test, post-test) mixed effects ANCOVA power analysis was conducted using the internal Monte Carlo simulation capabilities of Mplus (Version 1.20) under the following assumptions: 1) the attention control arm will show a  $d = 0.30$  effect size improvement in BA from pre-test to post-test, 2) based on the effect size obtained from pilot data analyses (i.e.,  $\eta^2 = 0.14$ ), the *SCThrive* intervention arm will show a  $d = 0.90$  effect size improvement from pre-test to post-test, 3) participants assigned to the *SCThrive* intervention arm will show an incremental effect of  $(0.90 - 0.30 = 0.60)$   $d = 0.60$  over participants assigned to the attention control arm, and 4) the inclusion of two control covariates (treatment type and baseline healthcare utilization), together with blocking on participant age and disease severity prior to randomization, will explain 40% (i.e.,  $R^2 = 0.40$ ) of post-test BA score variance. Results from the Monte Carlo simulation analyses based on 5,000 simulated datasets showed power will be  $> 0.80$  to detect the  $d = 0.60$  anticipated incremental improvement for the *SCThrive* intervention arm if recruitment,  $N = 64$ , results in a post-attrition  $N = 54$  ( $N = 27$  per group) available for statistical analysis.

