Self-management online portal. As part of her K-Award, the PI designed a web-based portal and examined the feasibility and preliminary efficacy of a six-week intervention to promote portal use in AYA with SCD aged 16-24. Data from 42 AYAs indicated that 95% found the portal easy to use, 90% found it beneficial, 98% reported that the portal increased SCD knowledge, and 95% reported that it improved their self-management. Yet, outcome data for BA and other measures were not impressive (pretest PAM-13 M=72.0; posttest PAM-13 M=65.6; i.e. no significant reduction in BA) suggesting that online-only interventions were unlikely to lead to measureable behavior change.

In-Person Delivery of SM Intervention for AYAs with SCD. The PI also conducted a pilot study of a six-week in-person group self-management intervention (Chronic Disease Self-Management Program – CDSMP) with 74 AYAs with SCD aged 16-24. Intervention participants were highly satisfied with the CDSMP (9.05 out of 10), yet barriers to regular attendance at sessions posed a strong impediment to study participation. Session completion was defined as 4/6 sessions; 34% of completers attended less than six sessions and another eight participants who started the intervention dropped out due to illness or family issues (e.g. hospitalization, family member ill). Participants rated sessions focused on physical activity and exercise, managing difficult emotions, and communicating with healthcare providers as most beneficial and reported that interacting with other AYA with SCD enhanced their ability to learn and continue to use self-management skills. Multivariate analyses found significant improvement from pre to post on AYA confidence in: 1) using exercise to deal with health problems ( $p = .005$ ), 2) keeping fatigue from interfering with pleasurable activities ( $p = .020$ ), and 3) exercising three times per week ( $p = .057$ ). Study findings are highly promising and suggest that in-person interventions have strong potential to improve AYA self-efficacy for self-management.

In summary, our pilot work underscores the need for multicomponent, peer-based interventions that include easily accessible technology enhanced tools combined with at least some in-person contact to enhance knowledge, peer support, and self-monitoring, but also to produce greater engagement and clinically significant changes in self-management in AYA with

[figure not shown]

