SCD Readiness to Change (AYA report)	SCD Readiness to Change for Self-Management Scale 	Measures amount of prior thought, knowledge, interest, anticipated difficulty and perceived importance about self-management; Mean Scores; N/A
Covariates		
Medical Covariates (EMR review)	Medical Background Case Report Form	ER visits, Hospitalizations, Treatment type
Demographic Covariates (AYA or Caregiver)	Demographics Form	AYAs age, gender, SES, SCD type, parental education, family income level
Treatment barriers (AYA or Caregiver)	Barriers to Care Questionnaire (BCQ) 	Sociobehavioral factors that interfere with successful interaction with the health care system

Table 3. Assessment Strategy		
Construct	Measure	Brief Description/Score Used/ Psychometrics
Psychosocial barriers (AYA or Caregiver)	Psychosocial Assessment Tool 74,95*	Assesses level of psychosocial risk for families of patients with a chronic illness
Feasibility & Acceptability		
Feasibility/ Acceptability/ Satisfaction (AYA report)	SCThrive Feasibility & Acceptability SCThrive Satisfaction Survey SCThrive Follow-up Questionnaire SCHealthED Feasibility & Acceptability	AYA opinion regarding the format, content, satisfaction and usefulness of SCThrive and SCHealthED
Feasibility/ Acceptability/ Satisfaction (AYA report)	iManage Feasibility & Acceptability Survey iManage Usage Survey	App characteristics, usefulness and computer/internet use
iManage Usability	Internet Background Questionnaire & Post Questionnaire	Assesses usability of the iManage app
SCThrive Group Qualitative Interview	SCThrive Feasibility Interview	Assesses usefulness and satisfaction with SCThrive in an interview format

\*Psychosocial Assessment Tool: Patients complete this annually during clinic visits in hematology. We will get permission from participants to use this data. We will only administer it if it has not been completed in the last 12 months. To decrease participant burden, we will then provide the PAT data to the clinic (so the participant will not have to complete it again – see consent form).

**Independent evaluators.** Trained independent evaluators blinded to treatment assignment (doctoral psychology graduate students) will administer self-management and treatment adherence measures (clinician ratings); one evaluator will review 25% of intervention sessions for fidelity.

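### The primary group-by-time test compares PAM-13 change, whereas the stated power above 0.80 matches a covariate-adjusted post-test comparison; adjusting for baseline PAM-13 would be more precise at almost no cost

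*Combined protocol and SAP*

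**What the plan says.** Section 9 (Aim 2) describes a two-group, two-wave model: "mixed ANCOVA analysis will be used, with BA (PAM-13) as our primary outcome, time and group as main effects", plus their interaction. Its stated purpose is "to determine the needed effect size estimates". The interaction carries the efficacy claim: "The statistical test of the interaction will be the primary tests of the efficacy of the SCThrive intervention". The model is called an ANCOVA, but the Aim 2 paragraph names no covariate, no covariate-by-time term and no adjustment for baseline PAM-13.

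The Power Analysis paragraph of the same section says the calculation was "conducted using the internal Monte Carlo simulation capabilities of Mplus", with 5,000 datasets. It assumes an incremental d of 0.60 (0.90 minus 0.30) and 54 analysed participants, 27 per group. It also assumes that "the inclusion of two control covariates (treatment type and baseline healthcare utilization), together with blocking on participant age and disease severity prior to randomization" explain 40% "of post-test BA score variance". Power is given as above 0.80.

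No alpha, sidedness, pre-post correlation or SD behind d is given. Section 3.1 reports pilot values as means only ("pretest PAM-13 M=72.0; posttest PAM-13 M=65.6"). Table 3 lists "ER visits, Hospitalizations, Treatment type" as medical covariates taken from the medical record.

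**The concern.** The power paragraph and the primary test appear to describe different comparisons. The 40% credit is defined on post-test scores. The primary test is on change, and a variable fixed at baseline that enters only as a main effect shifts both waves equally and drops out of change. The credit reaches the interaction only if covariate-by-time terms are in the model, and the Aim 2 paragraph does not list any.

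Separately, treating baseline PAM-13 as a repeated outcome instead of a covariate is the less precise option. Precision matters here because the trial is meant to produce effect sizes, and the Abstract says the results will support an application for a fully powered multisite trial. A wider interval is a poorer basis for planning that trial.

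**Working it through.** **Inputs from the documents (Section 9):** d = 0.60; n = 27 per arm; R² = 0.40 of post-test variance. **Assumed:** two-sided 5%; equal PAM-13 SDs at both waves, scaled to 1; d in raw-score SD units unless noted; pre-post correlation rho from 0.4 to 0.8; independent participants. Powers use the noncentral t distribution with noncentrality (0.60/√v)·√(27/2), where v is the residual variance.

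**1. The plan's own figure.** Take a post-test comparison with 40% of variance explained, so v = 1 − 0.40 = 0.60. Noncentrality is (0.60/0.775)·3.674 = 2.85. Power is 0.812 by normal approximation, 0.798 by noncentral t, and 0.796 after removing four covariate degrees of freedom. The normal-approximation sample size is exactly 27 per arm. The stated figure is therefore reproduced, to within rounding, as a post-test comparison.

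**2. The planned test and the alternative.** For change, v = 2(1 − rho), with 52 degrees of freedom. For post-test adjusted for baseline PAM-13 alone, v = 1 − rho², with 51. The variance ratio is (1 − rho²)/[2(1 − rho)] = (1 + rho)/2. The 95% half-width is t(0.975)·√(2v/27), in SD units.

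| rho | v, change | Power | Half-width | v, adjusted | Power | Half-width | Variance ratio |
|---|---|---|---|---|---|---|---|
| 0.4 | 1.20 | 0.51 | 0.598 | 0.84 | 0.66 | 0.501 | 0.70 |
| 0.5 | 1.00 | 0.58 | 0.546 | 0.75 | 0.71 | 0.473 | 0.75 |
| 0.6 | 0.80 | 0.68 | 0.488 | 0.64 | 0.77 | 0.437 | 0.80 |
| 0.7 | 0.60 | 0.80 | 0.423 | 0.51 | 0.86 | 0.390 | 0.85 |
| 0.8 | 0.40 | 0.93 | 0.345 | 0.36 | 0.95 | 0.328 | 0.90 |

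Without covariate help, 80% power needs rho of 0.70 for change and 0.64 for the baseline-adjusted model. At rho 0.70 the change variance is 2(0.30) = 0.60, the same residual variance as in step 1.

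**3. Covariate-by-time terms.** Let a be the share of pre-test variance the covariates explain, and c the overlap between the covariate combinations that predict pre-test and post-test. Residual change variance is then 2(1 − rho) − (a + 0.4 − 2c√(0.4a)), with 48 degrees of freedom. For the baseline-adjusted model with the same covariates it is 0.6 − (rho − c√(0.4a))²/(1 − a), with 47. Powers are at rho 0.4, 0.5, 0.6.

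| Assumed structure | Change variance removed | Interaction | Baseline-adjusted, same covariates |
|---|---|---|---|
| a = 0.40, c = 1 | 0 | 0.50, 0.58, 0.68 | 0.80, 0.81, 0.84 |
| a = 0.10, c = 1 | 0.10 | 0.54, 0.62, 0.73 | 0.83, 0.86, 0.91 |
| a = 0.10, c = 0.5 | 0.30 | 0.62, 0.73, 0.86 | 0.86, 0.91, 0.97 |
| a = 0.40, c = 0.5 | 0.40 | 0.68, 0.80, 0.93 | 0.84, 0.90, 0.96 |

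These values are analytic and ignore chance imbalance. The first row at rho 0.4 is an extreme corner: the covariance left between the waves is 0.4 − √(0.4·0.4) = 0.

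**4. If d is in change-SD units.** Power is 0.58 with no covariate credit, and 0.796 if the 40% is applied to change variance (v = 0.60, 48 degrees of freedom).

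**5. Limit of the gain.** In 20,000 simulated trials with four uninformative covariates, at rho 0.4 to 0.8, the interaction gave 0.510, 0.579, 0.675, 0.799, 0.934. The model with baseline PAM-13 and all four covariates gave 0.611, 0.657, 0.734, 0.821, 0.930. The advantage is gone by rho of about 0.8.

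**The case against.** The strongest reply has four parts.

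- **The power figure can be reconstructed.** This stands. The Power Analysis paragraph names the covariates and gives their joint R², and step 1 recovers about 0.80. A reader might infer that the figure is uncheckable altogether, or that the covariates are undisclosed. Neither is so. The gap is narrower: the place of those variables in the Aim 2 model, and whether the figure transfers to the interaction.
- **d may be on the change scale.** The plan derives it from an eta-squared for change in activation, so this reading is natural, and step 4 then gives about 0.80. But it requires the 40% to apply to change variance, whereas the plan ties it to post-test scores. Neither reading is settled. The ratio (1 + rho)/2 does not depend on the units of d, so the precision argument holds either way.
- **The simulation probably included a correlation.** It covered both waves, so some value was probably set, and it may have been favourable. That is a reason to report it.
- **SCThrive is delivered in groups.** Section 8 plans groups of four to eight, and the figures here treat participants as independent. The caveat is fair, but it applies equally to the planned test and does not remove the relative gain.

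It is also true that this is a pilot, and that the interaction is a valid test of the same arm difference under randomisation.

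**Conclusion.** The point holds as a mismatch between the power statement and the named test, together with an avoidable loss of precision. The figure above 0.80 carries over to the interaction under any of three unstated conditions: rho of about 0.70 with d in raw-score SD units; covariate-by-time terms that remove enough change variance (about 0.40 at rho 0.5, since 1.00 − 0.40 = 0.60); or d in change-SD units with the 40% applied to change.

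A reader might go further and infer that the trial is underpowered, that the stated power is wrong, or that the interaction test is invalid. The documents support none of these. No value of rho appears in them, and the range 0.4 to 0.8 is an assumption.

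The gain from baseline adjustment is 25% less variance at rho 0.5 (power 0.58 to 0.71) and 15% less at rho 0.7 (0.80 to 0.86), with equal SDs at both waves, two-sided 5%, and d in raw-score SD units for the powers. It shrinks as rho rises. This should be fixed, but it is not a fatal flaw.

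**What to change.** Make the primary analysis a linear model of post-treatment PAM-13 on arm, adjusted for baseline PAM-13, the age and severity strata, treatment type and baseline healthcare utilization. Report the adjusted arm difference with its 95% confidence interval, and keep the group-by-time test as supportive.

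State alpha, sidedness, the SD behind d and the assumed pre-post correlation. Restate power for the new model from the sponsor's own simulation inputs. No range should be prescribed from outside: with covariates, step 3 runs from 0.80 to 0.97 depending on structures the plan does not give. If the interaction stays primary, list any covariate-by-time terms and restate its power against the stated correlation.

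The cost is SAP wording. Baseline PAM-13 (Section 8, Assessment Strategy), the strata (Section 6, Recruitment) and the covariates (Table 3) are already collected, so no participants or visits are added. The downsides are about five degrees of freedom, a gain that disappears by rho of about 0.8 if the four extra covariates are uninformative, and possibly a less favourable stated power.

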*SCThrive arm.* Four successive groups with four to eight participants per group will be conducted. Participants will receive the finalized six-week *SCThrive* intervention using procedures described in Aim 1. To encourage retention and skill maintenance, participants will receive one online/in-person booster session two weeks after treatment ends. Based on feedback from the Intervention Development Team we will allow participants who cannot attend the in-person session due to illness or other factors to attend online via ZOOM. We will also allow participants to review a missed session recording before the next session with the CRC.

*Attention control arm.* Additional trained therapists (not conducting *SCThrive*) will conduct the attention control intervention which consists of six weekly 15-20 minute individual phone calls via Zoom. Participants will receive one online booster session two weeks after treatment ends.

*Assessment Strategy.* AYAs will complete questionnaires assessing BA, self-management behaviors (including healthy lifestyle behaviors), quality of life, and depressive symptoms (which can impact BA; Beck Depression Inventory-II), at baseline, post-treatment, and six-weeks after treatment (see Table 3). Caregivers or AYAs  $\geq$  age 18 will complete demographic (e.g. parental

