education, family income), psychosocial (Psychosocial Assessment Tool – PAT 2.0 General), barriers to care (Barriers to Care Questionnaire – BCQ) measures at baseline. Caregivers will also complete a quality of life measure at baseline and post-treatment. We will collect ER visits, disease severity, and hospitalization data from the EMR. *SCThrive* satisfaction and usefulness will be assessed after each session. Feasibility, acceptability, and *iManage* usage measures will be completed at post-treatment. The *iManage* tool will provide usage data on the number and frequency of logins, pages visited, time spent on each page, and number and time of action plan reminders. Based on feedback from the pilot group, we added a health motivation measure (Treatment Self-Regulation Questionnaire – TSRQ) to capture the social support and healthcare knowledge and skills participants reported were significant benefits of participating in the intervention. In addition, since our original submission an SCD-specific measure of self-management/ transition readiness has been published. We have now added these two measures to the battery and will increase our compensation accordingly. We also added a feasibility measure for the SHealthEd treatment and a qualitative interview for the SCThrive treatment to help us better understand participant perceptions and experiences with the intervention.

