**Table 3. Assessment Strategy**

Construct	Measure	Brief Description/Score Used/ Psychometrics
Primary Outcome Measure		
Behavioral Activation (BA) (AYA report)	PAM-13 	Measures skills, knowledge, confidence and readiness for self-management; Total Score; used in many studies of BA and self-management  ; $\alpha = .87$
Secondary and Exploratory Outcome Measures		
Self-management behaviors (AYA report)	TRAQ-5  ; Youth Risk Behavior Survey items 	Measures managing medications and appointments, tracking symptoms, provider communication, daily interference and physical activity, eating, sleeping and fluid intake; TRAQ Total Score ( $\alpha = .82-.92$ ) and Youth Risk Behavior Survey item mean scores; N/A
Self-management behaviors (clinician rating)	TRxANSIT Scale V4 	Semi-structured interview that assesses knowledge of chronic health condition, medications, adherence, nutrition, self-management skills, insurance, and finding a new health care provider); Knowledge of Chronic Health Condition, Medications, Adherence, Self-Management Skills Subscales; $r = .71$
Medication Adherence (clinician rating)	Medical Adherence Measure (MAM) 	Semi-structured interview with four general modules to assess adherence with medication, diet, exercise, and clinic attendance; Medication Domain; $r = -.40$ ; $r = .89$
SCD-specific quality of life (Caregiver & AYA report)	Peds-QL SCD Module 	Measures several domains of health-related quality of life including pain impact, fatigue, pain management, emotions, communication and treatment adherence; Total Score; $\alpha = .95$
SCD Knowledge (AYA report)	SCD Knowledge Questionnaire 	Measures SCD knowledge including pathophysiology, treatments and self-management; Total Score; $\alpha = .79$
SCD Self-Efficacy (AYA report)	Sickle Cell Self-Efficacy Scale 	SCD self-efficacy scale validated in adolescents with SCD; Total Score; $\alpha = .87$
Self-Regulation (AYA Report)	Treatment Self-Regulation Questionnaire (TSRQ)	Measures the degree of motivation an individual has towards changing/maintaining health behaviors; Total Score; $\alpha > .73$ .
SCD Transition Readiness	Transition Intervention Program Readiness for Transition (TIP-RFT)	Measures healthcare knowledge and skills, education and vocation planning, social support skill set, and independent living skills.

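### Section 9 runs the Aim 2 model to obtain effect sizes but calculates d only after significant tests, so a positive effect may go unreported and is overstated on average when reported

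*Combined protocol and SAP*

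**What the plan says.** All the operative text is in Section 9, Data Analysis/Methods.

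- **Purpose of the Aim 2 model.** The 2 (group) by 2 (time) mixed ANCOVA on PAM-13 is used "to determine the needed effect size estimates". No condition is attached to that phrase.
- **Primary test.** "The statistical test of the interaction will be the primary tests of the efficacy of the SCThrive intervention".
- **When d is calculated, Aim 2.** The sentence opens with the condition that the interaction is significant. It then provides d "for all significant simple main effects and simple comparison effect size calculations described above". No simple-comparison calculations are in fact described above it.
- **When d is calculated, Exploratory Aim.** "A significant omnibus test will be followed with simple comparisons and computation of effect size estimates (d").
- **Summaries without a condition.** Descriptive statistics, including means and standard deviations, "will be calculated for all measures of interest". The text does not say by arm or by visit.

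No section plans a confidence interval for d. The Abstract says the results will be the groundwork for a later grant application for a fully powered multisite trial.

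**The concern.** An effect size is the stated product of the Aim 2 model, and a pilot's estimate is most useful when it is available whatever the test shows. Followed as written, the plan supplies d when a test succeeds and not otherwise. That has two consequences when the true between-arm effect is positive. The estimate is absent from some trials. In the trials that do report it, it averages above the truth, because estimates that happened to fall low were filtered out.

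The Aim 2 sentence can be read in two ways: the interaction alone opens the gate, or the interaction and the simple effect must both be significant. The size of the problem differs between them, so both are worked below.

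**Working it through.** **Inputs from the documents.** 27 analysed per arm; pre-to-post changes of 0.90 and 0.30 SD, a difference of 0.60; covariates and blocking explaining R² = 0.40 of post-test variance; stated power above 0.80 (Section 9, Power Analysis). 14 per arm at follow-up (Section 4).

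**Assumptions.** Two-sided alpha 0.05 (none is stated). Pre-post correlation 0.7, varied from 0.5 to 0.8. At 0.7 the change-score variance is 2(1 − 0.7) = 0.60, which equals 1 − R². Means below are in units of the true PAM-13 SD.

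**1. The plan's own power.** The standard error is √0.60 × √(2/27) = 0.7746 × 0.2722 = 0.211, so the noncentrality is 0.60/0.211 = 2.85. Against t(52) = 2.007, power is 0.798; the normal approximation gives 0.812. This agrees with the plan to within rounding. An estimate must exceed 2.007 × 0.211 = 0.42 to be significant.

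**2. Gate on the interaction only** (simulated 2 × 2 trials):

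| Correlation | d reported | Mean contrast | Mean post-test difference | Mean control change |
|---|---|---|---|---|
| 0.5 | 58% | 0.78 | 0.69 | 0.21 |
| 0.7 | 80% | 0.67 | 0.64 | 0.26 |
| 0.8 | 93% | 0.63 | 0.61 | 0.29 |
| Truth | | 0.60 | 0.60 | 0.30 |

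At 0.7 the contrast is 0.67/0.60 = 1.12 times the truth.

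**3. Both gates** (interaction and post-test comparison significant). The result depends on how much post-test variance the covariates remove:

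| Covariates | Reported at 0.7 | Mean post-test d at 0.7 | Range over correlations 0.5-0.8 |
|---|---|---|---|
| Remove 40% at both visits | 68% | 0.69 | 54-76%; 0.72-0.68 |
| Explain nothing | 51% | 0.79 | 42-55%; 0.81-0.78 |

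The first row is closer to the plan, which credits R² = 0.40 to the post-test score. Applying it equally at both visits is an assumption.

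**4. A smaller true effect.** With a true increment of 0.30 (assumed), interaction gate and correlation 0.7, d is reported in about 29% of trials with mean contrast about 0.55, that is 0.55/0.30 = 1.8 times the truth.

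**5. No true between-arm effect.** With changes of 0.30 in both arms, the interaction is significant in 5.0% of trials and the mean reported contrast is 0.00.

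**6. Exploratory Aim, 14 per arm.** Besides the Youth Risk Behavior items, Table 3 gives six scores for the two constructs: the TRAQ total, four TRxANSIT subscales ("Knowledge of Chronic Health Condition, Medications, Adherence, Self-Management Skills Subscales") and the AYA PedsQL total. The AYA questionnaires are taken at follow-up ("AYAs will complete questionnaires assessing BA, self-management behaviors (including healthy lifestyle behaviors), quality of life, and depressive symptoms", Section 8). The caregiver PedsQL is not ("Caregivers will also complete a quality of life measure at baseline and post-treatment"). The timing of the clinician ratings is not stated, so two scores (the AYA totals) were also tried.

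For p scores, each differing by d SD with common correlation r, the noncentrality is 7·p·d²/(1 + (p − 1)r), referred to F with p and 28 − p − 1 degrees of freedom. Example, p = 6, d = 0.6, r = 0.5: 7 × 6 × 0.36/3.5 = 4.32, power 0.22.

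| Assumed d on every score | Omnibus power, p = 2 (r = 0.3; 0.5) | Omnibus power, p = 6 (r = 0.3; 0.5) | No d reported |
|---|---|---|---|
| 0.3 | 0.12; 0.11 | 0.10; 0.085 | 88-92% |
| 0.6 | 0.36; 0.32 | 0.31; 0.22 | 64-78% |
| 0.9 | 0.70; 0.64 | 0.66; 0.49 | 30-51% |

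**7. Interval widths if d is always reported.** Half-width = t(0.975) × √(1 − R²) × √(2/n). For n = 27: 0.42 (R² = 0.40). For n = 14: 0.60 (R² = 0.40) and 0.78 (R² = 0).

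**The case against.** The strongest reply is that the plan may not mean to gate the main effect size at all. The purpose phrase is unconditional, and the later sentence is garbled. It can be read as governing only the follow-up simple effects and leaving the group-by-time effect size free. That reading is open, so the point is partly a request for clarity. What it lacks is an operative sentence: nothing says that d for the contrast will be reported regardless, and no interval is planned on any reading.

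Second, the means and SDs are promised unconditionally. If given by arm and visit, they would let a reader rebuild a rough unadjusted d. They would not give the adjusted estimate or its interval.

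Third, at the planning values with the interaction gate alone, the loss is one trial in five and the inflation of the contrast is 12%. This stands. A reader might infer that d would usually be missing, or take 51% and 0.79 as the plan's own figures; those come from the two-gate reading with covariates that explain nothing, which is not what the power section assumes.

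Fourth, an omnibus test before follow-up comparisons is a conventional safeguard against multiplicity. That justifies keeping the MANOVA as a significance test, but not withholding estimates.

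**Conclusion.** The point holds in a limited form. Section 9 makes effect sizes a purpose of the Aim 2 model and then provides d only after significant tests. With a positive true effect, that leaves d missing in some trials and too high on average in the rest. For Aim 2 at the planning values the effect is modest under the interaction gate and larger under both gates. It becomes serious if the true increment is nearer 0.30. In the 14-per-arm follow-up, non-reporting is the main problem, but its size rests wholly on an assumed effect, since the documents give none for those outcomes. Alpha, the pre-post correlation and the equal covariate effect at both visits are also assumed.

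Three stronger inferences are not supported:

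- **That every reported effect is inflated.** With the interaction gate alone, the control-arm change is biased downward, and with no true between-arm effect the reported d is not shifted on average.
- **That the next trial will be sized on a biased d.** The Abstract speaks only of groundwork for an application; no section says this d will set a sample size.
- **That the primary test is affected.** The concern is with reporting of estimates, not with the validity of the interaction test.

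**What to change.** Reword Section 9 so that reporting d does not depend on a p-value:

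- For PAM-13 at post-treatment, report the adjusted group-by-time difference and d, each with a 95% CI.
- For each exploratory outcome at follow-up, report d with a 95% CI, labelled exploratory.
- Name the SD that standardises d, and give means and SDs by arm and visit.
- Keep the interaction test as primary and the MANOVA as the omnibus significance test; neither decides whether d is shown.

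If unconditional reporting was always intended, this only states it. The cost is some wording and a few table rows, with no change to design, sample size or the primary test. The downside is that the intervals will look wide, by the half-widths in step 7, which is an honest picture of what a pilot of this size can estimate.
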